4.2.3 Exploratory Endpoints

Changes in the *T. pedis* ISGA

5. INVESTIGATIONAL PRODUCT (IP) / STUDY MATERIALS

5.1 Investigational Product / Test Articles

Investigational Product	Doses per Subject
Cohort 1- dose 10^6 /ml CFUs of [REDACTED]	1 dose
Cohort 2- dose 10^7 /ml CFUs of [REDACTED]	1 dose
Cohort 3- dose 10^8 / ml CFUs of [REDACTED]	1 dose

5.2 Study Materials

Study Materials Provided by Investigational Site	Study Materials Provided by Sponsor	
Gloves	Dermapak for Fungal Culture	Bio Hazard Bags
Supplies for KOH Wet Mount (On site)	e-Swabs/vials or Zymo DNA Shield Collection Tubes	Cover Slips
Computer with internet access	Cotton Tip Applicators	Pipettors and Tips
	Supplies for KOH Wet Mount KOH + DSMO	Diluent Vials & Cohort Vials
	Topical anti-fungal agent	Racks (Mixing & Application)
	Subject Labels (Source Docs)	Cryoboxes
	Sample Labels (swabs / Dermapaks)	Study Binder and Study Forms/Logs
	Kimwipes	Curettes
	Absorbent bench surface liners	Polypropylene Cleanroom Wipes
	Racks	Photographs Equipment (Laptop & camera)
		Shipping Materials

6. STUDY PROCEDURES

6.1 Inclusion Criteria

Subjects must meet all of the following criteria to be **included** in the study:

1. Witnessed, signed informed consent approved by EC / IRB.
2. If required by local authorities a signed Health Information Portability and Accountability Act (HIPAA) authorization form which permits the use and disclosure of subject's individually identifiable health information.
3. Male Subjects of any race 18 years of age and older.
4. Subjects with a clear diagnosis of interdigital T. pedis: T. pedis interdigital defined as lesions localized to the interdigital spaces or predominantly interdigital, but interdigital but may extend to other areas of the foot (the non-interdigital lesions should not be hyperkeratotic, i.e., characteristic of Tinea pedis moccasin).

5. Provisionally confirmed diagnosis at baseline by a positive potassium hydroxide (KOH) wet mount at the clinical site.
6. The sum of the clinical signs and symptoms scores of the target lesion is at least 4, including a minimum score of at least 2 for erythema AND a minimum score of 2 for either scaling, fissures/ cracking or pruritus/burning (on a scale of 0-3, where 2 indicates moderate severity).

6.2 Exclusion Criteria

Subjects with the following will be **excluded** from this study:

1. Any dermatological conditions that could interfere with clinical evaluations.
2. Any underlying disease(s) or some other dermatological condition that requires the use of interfering topical or systemic therapy.
3. Subjects that have not undergone the specified washout period(s) for the following topical preparations or subjects who require the concurrent use of any of the following topical medications **applied to the foot:**

Topical astringents and abrasives	1 week
Topical antibiotics on the affected area	2 weeks
Anti-inflammatories, corticosteroids, topical immunomodulators	4 weeks

4. Subjects that have not undergone the specified washout period(s) for the following systemic medications or subjects who require the concurrent use of any of the following systemic medications:

Corticosteroids (including intramuscular injections)	4 weeks
Antibiotics	4 weeks
Antifungal agents	4 weeks
Systemic immunomodulators	4 weeks

5. Treatment of any type for cancer within the last 6 months.
6. History of any significant internal disease.
7. Subjects who are known to be allergic to any of the test product(s) or any components in the test product(s) or history of hypersensitivity or allergic reactions to any of the study preparations as described in the Investigator's Brochure.
8. AIDS or AIDS related complex by medical history
9. Known or suspected immune suppressive medications or diseases
10. Diabetes mellitus Type I or II by medical history

11. Peripheral vascular disease based on medical history.
12. Any subject not able to meet the study attendance requirements.
13. Subjects who have participated in any other trial of an investigational drug or device within 30 days prior to enrollment or participation in a research study concurrent with this study.

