Exclusion Criteria	
Subjects with the following will be excluded from this study:
 
1. Any dermatological conditions that could interfere with clinical evaluations.2. Any underlying disease(s) or some other dermatological condition that requires the use of interfering topical or systemic therapy.3. Subjects that have not undergone the specified washout period(s) for the following topical preparations or subjects who require the concurrent use of any of the following topical medications applied to the foot: 

Topical astringents and abrasives (e.g. Burrow's solution)	1 week	

Topical antibiotics and antifungal on the affected area (e.g. Neomycin, Miconazole, Clotrimazole, Terbinafine)	2 weeks	

Anti-inflammatories, corticosteroids, topical immunomodulators (e.g. Pimecrolimus, Tacrolimus)	4 weeks	

 
4. Subjects that have not undergone the specified washout period(s) for the following systemic medications or subjects who require the concurrent use of any of the following systemic medications: 

Corticosteroids (including intramuscular injections) (e.g. Triamcinolone acetonide)	4 weeks	

Antibiotics (e.g. Tetracycline, Cephalosporins, etc.) and/or Antifungal agents (e.g. Fluconazole, Itraconazole, Terbinafine, etc.)	4 weeks	

Systemic immunomodulators (e.g. Cyclophosphamide, Azathioprine, Biologicals-Monoclonal Antibodies)	4 weeks	

 
5. Treatment of any type of cancer within the last 6 months.6. History of any significant internal disease (which contraindicates use of live microbiome e.g. leukemia, liver failure, cardiovascular disease)	Topical astringents and abrasives (e.g. Burrow's solution)	1 week	Topical antibiotics and antifungal on the affected area (e.g. Neomycin, Miconazole, Clotrimazole, Terbinafine)	2 weeks	Anti-inflammatories, corticosteroids, topical immunomodulators (e.g. Pimecrolimus, Tacrolimus)	4 weeks	Corticosteroids (including intramuscular injections) (e.g. Triamcinolone acetonide)	4 weeks	Antibiotics (e.g. Tetracycline, Cephalosporins, etc.) and/or Antifungal agents (e.g. Fluconazole, Itraconazole, Terbinafine, etc.)	4 weeks	Systemic immunomodulators (e.g. Cyclophosphamide, Azathioprine, Biologicals-Monoclonal Antibodies)	4 weeks

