6.5.1 Screening Visit

Following written informed consent from each subject, the Investigator will determine whether subjects are eligible to participate in the study by performing screening tests and evaluations. This would include collecting demographic information, review of Inclusion and Exclusion criteria, medical history, concomitant medications, a KOH examination at the site and ISGA.

Screening and baseline visits can occur on the same day if no washout period is necessary. The baseline visit must be completed within 28 days of the screening visit.

At the Screening visit, continuous monitoring of concomitant medications, therapies and AEs throughout the study period will begin.

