6.8 Concomitant medication and Excluded Therapy

Usage of prescription or over the counter topical or systemic medications will be reported during the subject's participation in the study. The use of anti-fungal or antibacterial treatments in the past 4 weeks is an exclusion criterion.

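### The synopsis, section 6.2 and section 6.8 give different exclusion rules for prior topical antifungal use, and no reading makes all three agree

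*Combined protocol and SAP*

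**What the plan says.** Three places in the combined protocol and SAP set the rule on earlier antimicrobial use.

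- **Section 6.2, items 3 and 4.** The topical table has a row for "Topical antibiotics on the affected area", at 2 weeks, and no row for topical antifungals. The row "Antifungal agents", at 4 weeks, sits in the table for systemic medications.
- **Synopsis, exclusion item 3.** The matching topical row reads "Topical antibiotics and antifungal on the affected area (e.g. Neomycin, Miconazole, Clotrimazole, Terbinafine", at 2 weeks.
- **Section 6.8.** "The use of anti-fungal or antibacterial treatments in the past 4 weeks is an exclusion criterion". No route is given. The sentence before it begins "Usage of prescription or over the counter topical or systemic medications will be reported".

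Section 6.2, item 2 also bars subjects with an underlying disease or "some other dermatological condition that requires the use of interfering topical or systemic therapy", but sets no interval for past use.

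On the qualifying on-site KOH, inclusion 5 asks for a positive result at baseline. Table 3 places the test on Day 1 before dosing, from the target web space. Table 2 marks it in the Screen column only. The 6.5.2 Day 1 list for subjects with an earlier screening visit has no on-site KOH step.

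**The concern.** These are operative eligibility rules that the site must apply to every candidate. Recruitment is mainly from a dermatology practice (section 6.3), so earlier use of a topical antifungal is plausible, although the documents give no frequency. The rule also affects scheduling, because section 6.5.1 states: "Screening and baseline visits can occur on the same day if no washout period is necessary". Whether a recent user may be screened and dosed on one day therefore depends on which text is followed.

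The analytic stake lies in the section 4.2.2 endpoints: detection and abundance of T. rubrum, and conversion of culture and KOH to negative. Drug left on the skin from earlier treatment would push these in the same direction as a DBI-001 effect. With a single open-label arm at each dose level, no comparison could separate the two.

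**Working it through.** The plan states no figure to reproduce: section 6.14 makes no sample-size assumptions. The check sets the rules side by side and applies each to the same hypothetical subjects. Because 6.8 gives no route, it is taken both ways.

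**Step 1. The rule in each text (washout required).**

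| Text | Topical antifungal | Topical antibacterial | Systemic antifungal |
|---|---|---|---|
| 6.2, items 3 and 4 | not listed | 2 weeks | 4 weeks |
| Synopsis, items 3 and 4 | 2 weeks | 2 weeks | 4 weeks |
| 6.8, read as all routes | 4 weeks | 4 weeks | 4 weeks |
| 6.8, read as systemic only | silent | silent | 4 weeks |

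The systemic column agrees throughout. The trouble is confined to topicals.

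**Step 2. Apply the rules to topical antifungal use on the affected area.** A subject is excluded when the time since last use is shorter than the stated washout.

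| Last use | 6.2, item 3 | Synopsis | 6.8, all routes | 6.8, systemic only |
|---|---|---|---|---|
| 1 week before | not excluded | excluded (1 < 2) | excluded (1 < 4) | not excluded |
| 3 weeks before | not excluded | not excluded (3 > 2) | excluded (3 < 4) | not excluded |
| more than 4 weeks before | not excluded | not excluded | not excluded | not excluded |

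**Step 3. Apply the rules to a topical antibacterial last used 3 weeks before.** Section 6.2 and the synopsis both admit the subject (3 > 2). Section 6.8 excludes him (3 < 4) if it covers topicals.

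**Step 4. Look for a reading that removes the conflict.**

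- *6.8 covers all routes.* There are then three rules for topical antifungals (none, 2 weeks, 4 weeks) and two for topical antibacterials (2 and 4 weeks).
- *6.8 only restates the systemic rows.* Topical antibacterials then agree at 2 weeks, but 6.2 and the synopsis still differ on topical antifungals.
- *Antibiotics in 6.2, item 3 is meant to include antifungals.* Item 4 of the same section gives the two classes separate rows, so 6.2 does not use the word that way.
- *Item 2 fills the gap.* It concerns conditions that need interfering treatment and sets no interval for past use.

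None of these brings the three texts into line.

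**Step 5. On-site KOH, previously screened subjects only.** Inclusion 5 and Table 3 point to baseline or Day 1. Table 2 points to screening, and the Day 1 list for these subjects leaves the test out. Subjects screened and dosed on the same day are not affected: their Day 1 list has the test as step 10.

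**The case against.** The strongest reply is that exclusions accumulate. Section 6.8 is in the protocol body, calls the 4-week rule an exclusion criterion, and follows a sentence that names topical medicines. A site applying the whole protocol would then turn away anyone with topical antifungal use in the past 4 weeks, and the row in 6.2 would simply have lost a word. This has force, and for that reason a reader should not infer that the protocol as a whole knowingly admits current antifungal users; only 6.2 item 3, taken alone, fails to bar them. But the cumulative reading makes the 2-week topical antibiotic row in 6.2 and the synopsis pointless, and 6.8 never says that it overrides them.

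A second reply is that entry still needs a positive on-site KOH, an erythema score of at least 2 and a total score of at least 4, so a subject largely cleared by earlier treatment would not qualify. That limits the effect of residual drug without removing it.

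On the KOH, a reader might combine Table 2 with "The baseline visit must be completed within 28 days of the screening visit" and infer that a previously screened subject is dosed on a KOH up to 28 days old because no other on-site test is scheduled. The documents do not support that. Table 3 schedules a Day 1 pre-dose test for all subjects, section 6.5.2 opens by deferring to Tables 2 and 3, and eligibility is reviewed again on Day 1. The Screen column of Table 2 itself extends to Day 1, and nothing forbids testing at both visits. What stands is an omission from one list and one table column. It matters little, because central-laboratory culture and KOH are scheduled for everyone on Day 1.

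**Conclusion.** The contradiction on topical antifungals is real and rests on the text alone. For last use within 2 weeks, 6.2 item 3 and the synopsis disagree whatever 6.8 means. For last use between 2 and 4 weeks, eligibility turns on whether 6.8 covers topicals, which it does not say; the same question decides whether topical antibacterials have one rule or two.

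The consequence is moderate. It falls on secondary, descriptive microbiological endpoints in 12 uncontrolled subjects. A reader might infer that the safety conclusions or the move to the next dose are compromised. Nothing in the documents supports this: the primary objective is safety and tolerability, and escalation depends on the Day 7 safety review. The number of subjects affected cannot be estimated, and that residual antifungal would alter the results is a possibility, not something the documents establish.

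The KOH mismatch is minor. It concerns the consistency of the schedule, not the validity of the Day 1 central-laboratory baseline.

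**What to change.** 1. Reconcile synopsis exclusion item 3, section 6.2 items 3 and 4, and section 6.8 to one rule for topical antifungals and topical antibacterials. State it identically in each place, with the route. The interval is the sponsor's decision.
2. As a minor item, reconcile inclusion 5, Table 2, Table 3 and the 6.5.2 Day 1 list for previously screened subjects on when, and from which web space, the qualifying on-site KOH is taken.

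The cost is protocol wording. Depending on the rule the sponsor chooses, some recent topical users may have to wait or be excluded, which could slow recruitment of the 12 subjects. Depending on how item 2 is settled, previously screened subjects may need the on-site KOH added to their Day 1 list.

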6.3 Recruitment and Retention

Subjects will be recruited from the Investigator's clinical dermatology practice. The investigator may also recruit subjects using Ethics Committee approved recruitment materials. Retention is not anticipated to be an issue for this short 4-week trial.

6.4 Withdrawal or Termination

6.4.1 Subject Withdrawal

Participation in the study is strictly voluntary. A subject has the right to withdraw from the study at any time for any reason and is under no obligation to disclose the reason. If a subject withdraws, the Investigator and Sponsor are to be informed immediately and the withdrawal noted on the Case Report Form. Subjects may be replaced at the discretion of the Investigator and Sponsor.

The Investigator has the right to terminate participation of a subject at any time for any of the following:

- Use of non-permitted concomitant medication
- Lack of subject compliance
- Protocol violation
- Disease progression
- Any perceived safety risks

6.4.2 Study Discontinuation

There is only a single application per subject of the test article and drug product discontinuation is not anticipated.

Study discontinuation is at the discretion of the Sponsor or the Investigator in any of, but not limited to, the following events:

- Occurrence of unusual AEs in terms of their nature, severity, causality, duration, or unexpected incidence.
- Medical or ethical reasons affecting the continued performance of the study.
- Difficulties in the recruitment of the subjects.

6.4.3 Stopping Rules

With a single application per subjects there is no need for stopping rules for individual subjects. However, the sponsor may terminate dosing new subjects if there are safety concerns noted for any reason.

Table 2 Schedule of events for Subjects

Evaluation	*Screen (-28 day to day 1)	Day 1 / Baseline	1 Hr. after application	Day 2	Day 3 (+1)	Day 7 (+/-1)	Day 14 (+/-2)	Day 28 (+/-2)		
			Treatment period	Follow up period						
Informed consent	X	X								
Demographics	X	X								
Inclusion/Exclusion	X	X								
Medical History	X	X								
ISGA of T. pedis	X	X		X	X	X	X	X		
Clinical assessment of signs and symptoms of T. pedis		X		X	X	X	X	X		
Application of Investigational Product		X								
Concomitant Medication inquiry	X	X		X	X	X	X	X		

Evaluation	*Screen (-28 day to day 1)	Day 1 / Baseline	1 Hr. after application	Day 2	Day 3 (+1)	Day 7 (+/-1)	Day 14 (+/-2)	Day 28 (+/-2)
Application Site Reactions (local tolerability for areas unaffected by T. pedis)		X	X	X	X	X	X	X
Adverse Events		X	X	X	X	X	X	X
e-Swab		X	X	X	X	X	X	X
KOH Wet Mount (On Site)	X							
Fungal Culture & KOH (Mycology Central Lab)		X				X		X
Photos of T. Pedis		X				X	X	X

*Washout

6.5 Study Visits

The study will be conducted with a Screening visit that may also be Day 1 / Baseline visit, 1-hour after application evaluation and five follow-up visits. Further details on timing, administration of the assessment, and processes are provided in the Study Operation Manual (SOM).

6.5.1 Screening Visit

Following written informed consent from each subject, the Investigator will determine whether subjects are eligible to participate in the study by performing screening tests and evaluations. This would include collecting demographic information, review of Inclusion and Exclusion criteria, medical history, concomitant medications, a KOH examination at the site and ISGA.

Screening and baseline visits can occur on the same day if no washout period is necessary. The baseline visit must be completed within 28 days of the screening visit.

At the Screening visit, continuous monitoring of concomitant medications, therapies and AEs throughout the study period will begin.

6.5.2 All Other Visits

Study visit assessments will be conducted as presented in Tables 2 and 3.

a. Baseline (Day1) visit:

For subjects who did not have a screening washout period will have the following tasks completed at baseline Day 1:

1. Informed consent.
2. Record demographics.
3. Review of Inclusion/Exclusion Criteria.
4. Medical history.
5. Concomitant medication.
6. T. pedis ISGA of each web space on both feet.
7. T. pedis signs and symptoms.
8. Classification toe web space. As not all web spaces are equally affected and the act of collecting samples from a web space could affect the laboratory results. Web spaces on both feet will be classified based on the ISGA as clear, almost clear, mild T. pedis, moderate T. pedis, severe T. pedis. In addition, one representative web space classified

as moderate will be designated as the target sampling web space. Representative web space should be marked on each subject's paperwork for reference.

9. Signs and symptoms of local tolerability of the areas other than the web spaces.
10. Collect sample for onsite KOH from the target sampling web space.
11. Collect sample for reference mycology laboratory from the target sampling web space.
12. Collect an e-swab from the target sampling web space.
13. Obtain digital photograph of the target sampling web space.
14. Assigned test article will then be applied to both feet. Approximately 0.5 ml of the test article will be applied to each foot spreading the test article over all web spaces, on and around all toe nails, the entire plantar and lateral aspects of the foot.
15. Record any adverse event, if any.

16. One hour after application of the test article, the following activities will be done:

- a. E-Swab from an affected web space other than target sampling web space.
- b. Signs and symptoms of local tolerability of the areas other than the web spaces.
- c. Record adverse event, if any.
- d. Give an appointment for Day 2 visit.

For subjects **who had a screening** visit prior to a baseline visit before the test article is applied will have the following tasks completed:

1. Review of Inclusion/Exclusion Criteria.
2. Update Medical History.
3. Concomitant medications.
4. Record Adverse events, if any.
5. T. pedis ISGA of each web space on both feet.
6. T. pedis signs and symptoms.
7. Classification toe web space. As not all web spaces are equally affected and the act of collecting samples from a web space could affect the laboratory results. Web spaces on both feet will be classified based on the ISGA at clear, almost clear, mild T. pedis, moderate T. pedis, severe T. pedis. In addition, one representative web space classified as moderate will be designated as the target sampling web space.
8. Signs and symptoms of local tolerability of the areas other than the web spaces.
9. Collect sample for reference mycology laboratory from the target sampling web space
10. Collect an e-swab from the target sampling web space.
11. Obtain digital photograph of the target sampling web space.
12. Assigned test article will then be applied to both feet. Approximately 0.5 ml of the test article will be applied to each foot spreading the test article over all web spaces, on and around all toe nails, the entire plantar and lateral aspects of the foot

13. One hour after application of the test article, the following activities will be done:

- a. E-Swab from an affected web space other than target sampling web space.
- b. Signs and symptoms of local tolerability of the areas other than the web spaces
- c. Record adverse event, if any.
- d. Given an appointment for Day 2 visit.

Detailed instruction for sample collection and processing are in the Study Operation Manual, provided separately.

Day 2 Approximately 24 hours after the test article was applied:

1. Concomitant medications.
2. Adverse events.
3. T. pedis ISGA of each web space on both feet.
4. T. pedis signs and symptoms.
5. Signs and symptoms of local tolerability of the areas other than the web spaces.
6. Collect an e-swab from an affected but previously not sampled web space. If none available collect e-swab from an unaffected but previously not sampled web space.
7. Give subject appointment for Day 3 visit.

Detailed instruction for sample collection and processing are in the Study Operation Manual, provided separately.

Day 3 Approximately 48 hours after the test article was applied:

1. Concomitant medications.
2. Adverse events.
3. T. pedis ISGA of each web space on both feet.
4. T. pedis signs and symptoms.
5. Signs and symptoms of local tolerability of the areas other than the web spaces.
6. Collect an e-swab from an affected but previously not sampled web space. If none available collect e-swab from an unaffected but previously not sampled web space.

Detailed instruction for sample collection and processing are in the Study Operation Manual, provided separately.

Day 7

1. Concomitant medications.
2. Adverse events.
3. T. pedis ISGA of each web space on both feet.
4. T. pedis signs and symptoms.
5. Signs and symptoms of local tolerability of the areas other than the web spaces.

6. Collect sample for routine mycology from the target sampling web space.
7. Collect an e-swab from the target sampling web space.
8. Obtain digital photograph of the target sampling web space.

Detailed instruction for sample collection and processing are in the Study Operation Manual, provided separately.

Day 14

1. Concomitant medications.
2. Adverse events.
3. T. pedis ISGA of each web space on both feet.
4. T. pedis signs and symptoms.
5. Signs and symptoms of local tolerability of the areas other than the web spaces.
6. Collect an e-swab from the target sampling web space.
7. Obtain digital photograph of the target sampling web space.

Detailed instruction for sample collection and processing are in the Study Operation Manual, provided separately.

Day 28

1. Concomitant medications.
2. Adverse events.
3. T. pedis ISGA of each web space on both feet.
4. T. pedis signs and symptoms.
5. Signs and symptoms of local tolerability of the areas other than the web spaces.
6. Collect for routine mycology from the target sampling web space.
7. Collect an e-swab from the target sampling web space.
8. Obtain digital photograph of the target sampling web space.

Detailed instruction for sample collection and processing are in the Study Operation Manual, provided separately.

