4. STUDY DESIGN AND ENDPOINTS

4.1 Description of the Study Design

A single center open label dose escalating study design will be used in a population of patients with interdigital *Tinea pedis*. Each subject will have a single application of approximately 0.5 ml of the test article applied to each foot covering the web spaces of both feet as well as the plantar and lateral aspect of both feet as well as on and around all toes and toe nails. The three test articles will be 10^6 CFUs/ml, 10^7 CFUs/ml, and 10^8 CFUs/ml. Each of the three groups will have 4 subjects. After the first cohort has completed their day 7 visits and if no significant tolerability of safety issues is identified the second cohort will be enrolled. After the second cohort has completed the day 7 visits and if no significant tolerability or safety issues are identified the third cohort will be enrolled.

Evaluations will be followed according to Table 2 Schedule of Events for Subjects. At all evaluations, signs and symptoms of application site reactions (local tolerability at sites unaffected by *T.pedis* interdigital) will be recorded. At baseline, days 2, 3 (+1), 7 (+/-1), 14 (+/-2), and 28 (+/-2), the signs and symptoms of *T. pedis* will be recorded. The investigators static global assessment (ISGA) of the interdigital *T. pedis* will be recorded at baseline, days 2, 3(+1), 7 (+/-1), 14 (+/-2), and 28 (+/-2). Subjects will also be queried for adverse events during their follow up visits or by self-reporting while on study until Day 28.

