4.2 Study Endpoints

4.2.1 Primary Endpoints

a. Safety

- Tolerability will be evaluated through assessment of selected local signs and symptoms (pain / burning / stinging, pruritus, erythema, edema, and scabbing / crusting). Any local skin reaction that requires use of a concomitant therapy or study discontinuation should be reported as an AE on the Case Report Forms.

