6.6.3 Local Tolerability for Areas Not Affected by T. Pedis

Local tolerability for areas to which the test article is to be applied but without T. pedis such as the unaffected web spaces on and around the toes, toe nails, the plantar and lateral aspects of the foot tolerability will be evaluated based on these signs and symptoms:

Pain/Burning: as reported by the subject as being the greatest intensity they have experienced within the last 24 hours at Baseline or since the last visit at subsequent visits.

0	None	No pain/burning
1	Mild	Slight burning/stinging sensation; not really bothersome
2	Moderate	Definite warm, burning/stinging that is somewhat bothersome
3	Severe	Hot burning/stinging sensation that causes definite discomfort and may interrupt daily activities and/or sleep

Pruritus: as reported by the subject as being the greatest intensity they have experienced within the last 24 hours at Baseline or since the last visit at subsequent visits.

0	None	No pruritus
1	Mild	Slight pruritus, not really bothersome
2	Moderate	Definite pruritus that is somewhat bothersome
3	Severe	Intense pruritus that may interrupt daily activities and/or sleep

Erythema: as assessed by the Investigator

0	None	No erythema present
1	Mild	Slight pink coloration
2	Moderate	Definite redness
3	Severe	Marked erythema, bright red to dusky dark red in color

Edema: as assessed by the Investigator

0	None	No edema
1	Mild	Slight, but definite edema
2	Moderate	Definite edema
3	Severe	Marked edema

Scabbing/Crusting: as assessed by the Investigator

0	None	No scabbing/crusting
1	Mild	Slight, but definite scabbing/crusting
2	Moderate	Definite scabbing/crusting
3	Severe	Marked scabbing/crusting

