7. ASSESSMENT OF SAFETY

7.1 Safety Evaluations and Criteria

Upon completion of the day 7 visit by the first cohort, the Medical Monitor and Investigator will review the safety results and determine if the trial is to proceed with dosing the second cohort. The same process will be completed upon completion of Day 7 for Cohort 2 to determine if Cohort 3 will be enrolled.

As detailed in section 6.6.3, local tolerability will be evaluated by recording the severity of the signs of *T. pedis* as well as the signs and symptoms of local tolerability on treated areas not involved with *T. pedis*. In addition, adverse events will be documented.

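### The visit steps leave unaffected web spaces off the primary tolerability scale, against Table 2 and section 6.6.3; affected web spaces have no scheduled edema or crusting score

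*Combined protocol and SAP*

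**What the plan says.** Section 4.2.1 defines the primary endpoint by five local signs and symptoms ("pain / burning / stinging, pruritus, erythema, edema, and scabbing / crusting") and sets no limit on site. Section 6.6.3 gives the 0-3 grades. The sections then say where the scale applies:

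- **6.5.2, visit steps** (Baseline, 1 hour, Days 2, 3, 7, 14 and 28): "Signs and symptoms of local tolerability of the areas other than the web spaces".
- **Table 2**, same seven times: "Application Site Reactions (local tolerability for areas unaffected by T. pedis").
- **4.1**, at all evaluations: "signs and symptoms of application site reactions (local tolerability at sites unaffected by *T.pedis* interdigital) will be recorded".
- **6.6.3**, which defines the scale: "Local tolerability for areas to which the test article is to be applied but without T. pedis such as the unaffected web spaces", followed by the toes, toe nails, plantar and lateral foot.
- **7.1**: local tolerability comprises the severity of T. pedis signs plus tolerability on treated skin not involved with T. pedis. It gives 6.6.3 as the source, but T. pedis signs are graded in 6.6.1.

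Section 6.5.2 opens with "Study visit assessments will be conducted as presented in Tables 2 and 3".

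Product is applied to all web spaces, affected or not. On affected web spaces the scheduled instruments are the 6.6.1 grading and the ISGA (6.6.2). Neither includes edema or scabbing/crusting, and neither is scheduled at 1 hour.

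**The concern.** The 6.5.2 step is repeated in every visit list, and those lists are what site staff work through. Taken as written, it removes every web space from the primary scale, including the unaffected ones that 6.6.3 names. The descriptive tolerability tables would then cover less treated skin than Table 2 and 6.6.3 intend.

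The second matter concerns affected web spaces. Section 2.1 lists worsening T. pedis, impetigo and cellulitis as possible effects, and the Medical Monitor and Investigator review safety at Day 7 before each ten-fold escalation. For affected web spaces, that review has no scheduled edema or crusting score to set against baseline. A reaction at 1 hour that resolves before Day 2 is left to adverse event recording.

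**Working it through.** The protocol gives no figure to reproduce: analysis is descriptive and 6.14 makes no sample size assumption. The check is a count of scheduled scores.

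**Inputs.** Scoring times: Baseline, 1 h, Days 2, 3, 7, 14, 28 = 7 (Table 2 and 6.5.2 agree); 5 of these fall up to the Day 7 review. Primary items: 5 (4.2.1). The 6.6.1 grading is scheduled at all times except 1 h = 6. Subjects: 3 cohorts × 4 = 12, each with an affected target web space (6.6.4).

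**Step 1. Scheduled uses of the five-item scale, by skin.**

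| Treated skin | Table 2 / 4.1 / 6.6.3 | 6.5.2 step as written |
|---|---|---|
| Unaffected, outside web spaces | 7 | 7 |
| Unaffected web spaces | 7 | 0 |
| Affected web spaces | 0 | 0 |

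The operative discrepancy is the second row. Under the literal step, unaffected web spaces keep an ISGA (which includes erythema) at 6 of 7 times, any 6.6.1 scores taken there, and adverse event recording.

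**Step 2. Affected web spaces: primary items with some scheduled score.**

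| Item | Graded in 6.6.1? | All times | Up to Day 7 |
|---|---|---|---|
| Erythema | Yes | 6 of 7 | 4 of 5 |
| Pruritus | Yes | 6 of 7 | 4 of 5 |
| Pain/burning/stinging | As burning/stinging | 6 of 7 | 4 of 5 |
| Edema | No | 0 of 7 | 0 of 5 |
| Scabbing/crusting | No | 0 of 7 | 0 of 5 |

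Item-by-time cells: 5 × 7 = 35. Scored: 3 × 6 = 18. Unscored: 2 × 7 + 3 × 1 = 17. The unscored cells include 2 of 5 items at Baseline and 5 of 5 at 1 h.

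Two assumptions apply. First, 6.6.1 burning/stinging is taken as equivalent to pain/burning/stinging, although 6.6.1 does not name pain. Second, 6.6.1 is taken as scored at all affected web spaces. The visit step names no site, and inclusion criterion 6 refers to the target lesion.

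**Step 3. What else records reactions on affected web spaces.** Adverse events are recorded at 1 h and every later visit. Photographs are taken at Baseline and Day 7 (2 of the 5 times); 6.5.2 specifies the target web space, while Table 2 does not limit the site. The 6.6.3 symptom items ask for the worst intensity since the last visit. Section 6.6.1 states no recall period, so a Day 2 grade need not recover a 1 h reaction.

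**The case against.** **The intended site can be inferred.** A reader might conclude that the protocol leaves the scoring site undetermined. The documents do not support that. Section 6.5.2 defers to Table 2; Table 2, 4.1, 6.6.3 and the second half of 7.1 agree; and the 6.5.2 step is the only outlier. With one centre and 12 subjects, practice may also be uniform. This stands, and it makes the Table 2 reading the probable one. It does not make the step correct, because the step contradicts the table at every visit.

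**Lesions beyond the web spaces.** Section 6.1 allows disease that "may extend to other areas of the foot", so the literal step could be said to score such lesions 7 times against 0 under Table 2. That would mean applying a scale titled for unaffected skin to T. pedis lesions, so it should not be counted as an equal rival reading.

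**Affected skin is not unobserved.** A reader might infer that the Day 7 review is blind to affected web spaces. It is not. Section 7.1 treats T. pedis signs as part of tolerability, and using different instruments for involved and uninvolved skin may be deliberate. Worsening T. pedis is tracked by 6.6.1 and the ISGA at Baseline and Days 2, 3 and 7. The adverse event definition (7.2) covers a previous condition that becomes more severe. Onset and resolution dates and maximum severity are recorded, and a local reaction needing concomitant therapy must be reported. What remains is narrower: the adverse event grade (7.5) measures tolerance and interference with daily activity, not sign severity on the 0-3 scale, and it supplies no baseline.

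**The Study Operation Manual** may add detail on assessments. It is not among the documents, and it would not by itself reconcile conflicting protocol text.

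**Conclusion.** The main point holds as an error of wording with a real consequence. Followed literally, the 6.5.2 step takes treated, unaffected web spaces from 7 scheduled primary-scale scorings to 0, against Table 2, 4.1 and 6.6.3. The 7.1 cross-reference is also wrong for T. pedis signs. Both should be corrected, since they decide which skin enters the primary endpoint.

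The second point is a gap rather than a contradiction, and filling it is an improvement of lower priority. On affected web spaces, under every version of the text, 17 of 35 item-by-time cells have no scheduled score, in all 12 planned subjects and on the assumptions stated with the tables. These counts describe the schedule. They do not estimate missed events, and they do not show that the escalation reviews lack safety information on these sites.

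**What to change.** **Main correction.**

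1. Reword the 6.5.2 step at all seven times to: local tolerability (6.6.3) of all treated skin unaffected by T. pedis, including unaffected web spaces.
2. Fix each area's affected or unaffected status at Baseline, and state which ISGA grades make a web space affected.
3. Have 7.1 cite both 6.6.1 and 6.6.3.

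This costs protocol and CRF wording only.

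**Secondary improvement, for affected treated skin.** Record one worst grade for edema and one for scabbing/crusting (6.6.3 grades) at the same seven times. Grade erythema, pruritus and burning/stinging (6.6.1) at 1 h. State which sites 6.6.1 covers. Report these scores separately as change from baseline, and include them in the Day 7 review.

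| Option | Per subject | 12 subjects |
|---|---|---|
| One worst grade per item | 2 × 7 + 3 × 1 = 17 | 204 |
| Same, if 6.6.1 covers only the target lesion | 17 + 3 × 6 = 35 | 420 |
| Each web space (8 assumed) | 17 × 8 = 136 | 1,632 |
| Each web space, 6.6.1 target lesion only | 17 × 8 + 18 × 7 = 262 | 3,144 |

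The documents give no web space count; 8 is an assumption (4 per foot). Scoring each web space is not needed. No new scale, staff or visit is required, and at 1 h an affected web space is already being swabbed.

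The drawbacks should be accepted openly. Scores on affected skin are partly confounded with disease, and there is no control group to separate the two. Target-lesion erythema is at least 2 of 3 at entry, so it can rise by at most one grade. A single worst grade loses location.
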